3.0 Study Design and Population

3.1 Number of Clinical Sites and Subjects

The REVIVE-IT Registry (i.e., REVIVAL) is a prospective cohort study to be conducted in up to twenty five (25) participating Clinical Sites in the USA. The study will continue until up to 400 eligible heart failure heart failure subjects have been enrolled (estimated length of accrual is 12 months). No single Clinical Site will enroll more than 80 heart failure subjects into the study without written approval from the Data Coordinating Center (DCC).

The REVIVE-IT Registry has been designed to provide a high likelihood of successful recruitment of the targeted 400 subjects at up to 25 study sites. The subject recruitment experience in the REVIVE-IT Trial and in MedaMACS, a registry with similar design and aims to the REVIVE-IT Registry, has informed the design of the REVIVE-IT Registry. Eligibility criteria have been expanded to no longer exclude patients who are on the heart transplant waiting list and those not yet listed who are heart transplant eligible. The pool of heart transplant listed patients alone who would be eligible for the REVIVE-IT Registry constitutes a substantial group of individuals (estimated at 30-75 per study site). These individuals may potentially benefit from

early implantation of an LVAD, so their inclusion in this registry is appropriate. Inclusion criteria have also been broadened to provide a larger pool of eligible advanced heart failure patients. For example, the REVIVE-IT Registry will enroll individuals with any of the following high-risk criteria – peak VO₂ \leq 14 ml/min/kg, 6 minute walk distance < 350 meters, serum sodium \leq 135 mg/dL, serum BNP \leq 750, serum NT-proBNP \leq 3000, HFSS \leq 7.19 or SHFM predicted mortality \leq 85% – whereas the REVIVE-IT trial required both a peak VO₂ \leq 14 ml/min/kg and a 6 minute walk distance < 350 meters. In recognition of the well-described limitations of the NYHA classification system (i.e., its very poor interobserver and intraobserver variability), we have broadened the inclusion criteria to ambulatory symptomatic heart failure patients (NYHA classes II-IV), rather than NYHA class III alone, and now rely firmly on more objective and well validated criteria (as above) to identify potential subjects with advanced heart failure.

3.2 Design

All enrolled heart failure subjects will be followed and assessed for outcomes for two (2) years post enrollment. The following events will be assessed at all but the baseline A visit:

- Hospitalizations
- Stroke
- Mechanical Circulatory Support Device (MCSD)*
- Transplant*
- Death (Cardiovascular related vs. Non-cardiovascular related)*

* Outcomes of death, transplant and implants of a durable VAD will be considered study endpoints with no additional follow-up in REVIVAL. When a study endpoint has been reached, events/outcomes up through the point of the outcome will be reported on the eCRFs.

3.3 Subject Identification Procedures

Medical records should be reviewed to assess for potential enrollment into the REVIVE-IT Registry. Heart failure subjects that meet all criteria (Sections 5.1 and 5.2) should be approached to consent for this study.

No group of persons will be excluded without a good scientific or ethical reason to do so. Incarcerated prisoners have been excluded by this protocol. Select data on all heart failure subjects who are approached who are ineligible (do not meet at least one inclusion or exclusion criterion) or who refuse participation in the study will be collected in a screening log. This basic information is necessary to assess completeness of heart failure subject capture and possible bias in the screening process and in the process of obtaining informed consent. No further information will be collected on heart failure subjects who do not meet the eligibility criteria or who refuse to consent to participate in the study.

3.4 Study Visit Overview

Enrolled heart failure subjects will undergo the following Schedule for Assessments.

- 1. Clinic visits: Baseline A, Baseline B and follow up visits at 6,12,18 and 24 months. All study visits will be in person.
- 2. See Schedule of Observations and Procedures (Section 6.0) and Time and Event Schedule (Appendix A) for details regarding visit specific assessments.

3.5 **Participating Centers**

Each of the Clinical Sites and Core Laboratories selected for REVIVAL represent experienced centers in the treatment of advanced heart failure.

4.0 Study Procedures and Assessments

4.1 Informed Consent Procedures

All REVIVAL heart failure subjects must be consented utilizing an IRB approved consent form with language that is understandable to them. Heart failure subjects must give Informed Consent to participate in the study as well as the main biomarker specimen collection, and separately may consent for genomic analysis.

All Caregivers must be consented utilizing an IRB approved consent form with language that is understandable to them. Caregiver contact details will be supplied from the heart failure subject at the first baseline visit. Consenting caregivers via mail will be permitted if this method is approved by the participating site's local IRB. Caregivers must give Informed Consent for REVIVAL prior to completion of the Caregiver Questionnaires.

If a Caregiver decides not to participate in REVIVAL, the heart failure subject will still be eligible to participate.

4.2 Six Minute Walk Test Distance (6MWT)

The 6MWT distance will be used as an eligibility criterion for potential heart failure subjects who have not had at least two heart failure related hospitalizations in the past year. The 6MWT assessment will be performed at baseline A and B and at each follow up visit. The 6MWT is a valid measurement of functional capacity and is predictive of outcomes in heart failure. The inability to walk > 350 meters is representative of poor functional class and increased morbidity and mortality in heart failure.^[18] The 6MWT evaluates the global and integrated responses of all the systems involved during exercise, including the pulmonary and cardiovascular systems, systemic circulation, peripheral circulation, blood, neuromuscular units and muscle metabolism. The 6MWT is a sub-maximal exercise test that is associated with smaller increments in heart rate, blood pressure and plasma catecholamines than maximal cardiopulmonary exercise testing, although in many ambulatory patients with advanced heart failure it may represent effort close to anaerobic threshold.^[19] However, such submaximal exercise may be more reflective of

activities of daily living and has been found to more closely correlate with formal measures of Heart Failure Quality of Life (HFQOL) than peak VO_2 . Despite the difference between these two functional tests, a significant correlation between 6MWT and peak VO_2 has been reported for patients.^[20-22]

4.3 Maximal Oxygen Consumption (peak VO₂)

Maximal treadmill cardiopulmonary exercise tests (CPX) will be done for consented heart failure subjects at the baseline B visit. Maximal oxygen consumption (peak VO₂) during treadmill CPX is the most objective and well-validated measure of functional capacity.^[23] Its depression reflects the impaired ability to increase cardiac output and is an integrated measure of the cardiac, pulmonary, vascular and muscular abnormalities that characterize heart failure. While not completely effort-dependent, the adequacy of the effort as maximal can be determined.

The reliability of peak VO₂ measurement in the setting of stable outpatients with chronic heart failure has recently been assessed in 398 subjects participating in an HF-ACTION sub-study with test-retest measurements 1-2 weeks apart.^[24] The difference (mean \pm SD) in peak VO₂ measurement was 0.0±1.3 ml/min/kg (10th,90th percentile = 0.1,3.0) with nominal increases in 46% and decreases in 48% of subjects. This SD of 1.3 represented 9% of the mean peak VO₂ of these subjects. These data demonstrate the reproducibility of the peak VO₂ measurement and support the strategy of using a single measurement of peak VO₂ as an eligibility criterion in REVIVAL.

Maximal treadmill cardiopulmonary exercise testing is invaluable in the assessment of functional limitations imposed by heart failure and in predicting survival in patients referred for cardiac transplant evaluation. ^[19] [name] performed the landmark study demonstrating the utility of a peak VO₂ threshold of 14 ml/min/kg for selecting heart transplant candidates.^[25] At Columbia University, 396 patients age 65 years or older (mean + SD = 70±5) with systolic (80%) or diastolic heart failure (LVEF 30±15%, peak VO₂ 13.9±4.4 ml/min/kg) were followed until death (35%), urgent transplantation (8.8%), LVAD (3.0%) or elective transplantation (2.3%). Overall 1-year event-free survival was 81%. As seen in Figure 2, individuals with peak VO₂ 10-14 ml/min/kg and < 10 ml/min/kg had event-free survivals of ≈78% and ≈70% at 1-year and ≈60% and ≈45% at 2-years, respectively.^[26]

Figure 2: individuals with peak VO₂ 10-14 ml/min/kg and < 10 ml/min/kg had event-free survivals of \approx 78% and \approx 70% at 1-year and \approx 60% and \approx 45% at 2-years, respectively.

4.4 Echocardiogram

At the baseline B visit, echocardiograms will be performed and DICOM data will be sent to the Echocardiography Core Lab for assessment of key elements. Details of data dissemination from the core lab to the clinical sites will be outlined in the MOP.

Rigorous echocardiographic quantification of cardiac structure and function is essential to prognosis in heart failure patients. This proposal is to demonstrate the importance of an echo core lab to quantify left ventricular (LV) and right ventricular (RV) function, along with valvular pathology and non-invasive hemodynamic measures.

The Echocardiography Core Lab will provide standardized and validated measurements of left ventricular (LV) and right ventricular (RV) function. In addition to having a proven track record with obtaining high quality routine echocardiographic measures, like ejection fraction (EF), the Echocardiography Core Lab also has extensive experience with innovations in strain imaging, using routine digital echocardiographic data, which can be immediately applied to multicenter clinical trials. An increase in as little as 5 EF units was highly statistically associated with heart failure hospitalizations in the EchoCRT randomized clinical trial.^[27]

4.5 Directed History, Physicals and Vital Signs

Directed history and physicals (including NYHA and INTERMACS Patient Profile) will be performed at baseline A and B visits and at each follow up visit. Mandatory data elements pertaining to these assessments will be detailed on the study eCRFs.

INTERMACS Patient Profile classifications (refer to Appendix B) and NYHA classifications (refer to Appendix C) will be obtained for heart failure subjects at each visit for REVIVAL.

Vital signs including height (collected only at baseline A), weight, heart rate, blood pressure and temperature will be performed at every study visit.

4.6 Medication Criterion

Heart failure subjects should be receiving appropriate evidenced-based heart failure medications – ACE inhibitor, ARB or sacubitril/valsartan [LCZ-696]; beta blocker; aldosterone antagonist; hydralazine/long-acting nitrate [required of African-American subjects only] for \geq 3 months absent contraindications or intolerances.

All heart failure therapeutics and dosages should be documented in the Case Report Forms (CRFs). Details of heart failure medications will be collected at each visit.

4.7 Handgrip Strength (by Dynamometer)

Handgrip strength will be assessed by dynamometer at each visit. Mandatory data elements pertaining to this assessment will be detailed on the study eCRFs. Instructions relevant to the assessment will be included in the MOP.

4.8 Gait Speed Test

A fifteen-foot gait speed test to measure frailty will be performed at each visit. Mandatory data elements pertaining to this assessment will be detailed on the study eCRFs. Instructions relevant to the assessment will be included in the MOP.

4.9 Demographics

Demographic information will be recorded in the study database after consent. In cases where Institutional restrictions limit reporting any component of demographic data, the DCC should be contacted to discuss reporting options. Caregiver contact information (i.e., name, address, phone and email) will be collected to allow for follow-up at the DCC. HIC numbers (if applicable for the subject) and partial social security numbers will be collected from heart failure subjects.

4.10 Documentation of Concomitant Medications

Concomitant medications will be monitored at all study visits and changes will be recorded on the eCRFs.

4.11 Documentation of Study Events/Outcomes

Adverse events related to study procedures and outcomes will be recorded on the study eCRFs. These will be recorded using data available in the medical chart as well as information gathered on patient diaries. Diaries will be provided to all heart failure subjects at the baseline A visit to provide a convenient way for the heart failure subject to capture key details about events/outcomes. Adverse event and outcomes data will be collected at all visits following the baseline A visit and in cases of early subject termination.

4.12 Seattle Heart Failure Model (SHFM) Score

The SHFM will be calculated by the Data Coordinating Center using data collected at baseline A, baseline B and the twelve (12) month follow up visit. Instructions relevant to the calculation will be included in the MOP.

4.13 Heart Failure Survival Score (HFSS)

The HFSS will be calculated by the Data Coordinating Center using data collected at baseline B. Instructions relevant to the calculation will be included in the MOP.

4.14 Health Status, Patient Perspective and Quality of Life Assessments

This study will use the following health status and QOL assessments:

- a. Heart failure-related QOL (KCCQ)
- b. EuroQoL (EQ-5D)
- c. State-Trait Anxiety Inventory (STAI)
- d. Depression (Personal Health Questionnaire [PHQ-8])
- e. Patient Preferences for end of life care and thresholds for VAD implantation (MEDAMACS VAD Survey)
- f. Caregiver Health QOL (EQ-5D)
- g. Caregiver Oberst Caregiving Burden Scale [OCBS])
- h. Caregiver Health History

QOL assessments will be provided to subjects in English. If a subject does not have proficiency in English, the subject remains eligible for the registry but should not complete the forms.

All heart failure subject QOL assessments and health utility assessment will be administered at all REVIVAL visits. The patient preference questionnaires will also be administered at all visits.

The Caregiver questionnaires will be provided to the heart failure subject's caregiver at the time of the baseline B visit and at each follow up visit. The questionnaires may be mailed to them by the DCC. Detailed instructions for completion of caregiver questionnaires are available in the MOP.

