6.2 Study Procedures and Assessments

6.2.1 Baseline A

Initiation of baseline A will occur with the heart failure subject signing the Informed Consent document(s). Standard of Care (SOC) testing will be included in the heart failure subject evaluation for this visit. All SOC procedures are labeled as such below. All other procedures will be research expenses. After signing the informed consent document(s), subjects will undergo the following testing and evaluation:

- 1. Directed history and physical (including NYHA and INTERMACS Patient Profile)
- 2. ECG (SOC)
- 3. Blood draw for:
 - a. CBC with platelets and differential count [SOC]
 - b. Comprehensive metabolic panel [SOC]
 - c. Uric Acid
 - d. Total cholesterol
 - e. INR
- 4. Handgrip strength (by dynamometer)
- 5. Gait Speed Test
- 6. 6 minute walk test
- 7. Quality of life and health utility questionnaires
- 8. Patient preference questionnaire
- 9. Caregiver participation overview with heart failure subject
- 10. Dispense patient diary

If the heart failure subject has an historic ECG on file that was completed within 30 days of the assessment date, this may be used for fulfillment of this visit requirement if, in the opinion of the investigator, the historic ECG is highly likely to represent the subject's current health status.

If the heart failure subject has historic laboratory results on file that were drawn within 14 days of the assessment date, these results may be used for fulfillment of this visit requirement if, in the opinion of the investigator, the historic laboratory result(s) are highly likely to represent the subject's current health status.

Baseline A procedures should be completed within two weeks of consent. The baseline B visit should be scheduled to occur two (2) months (\pm 30 days) after consent.

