6.2.2 Baseline B

Standard of Care [SOC] testing will be included in the heart failure subject evaluation for this visit. All SOC procedures are labeled as such below. For the baseline B visit, subjects will undergo the following testing and evaluation:

- 1. Directed history and physical (including NYHA and INTERMACS Patient Profile)
- 2. ECG [SOC]
- 3. Blood draw for:
 - a. CBC with platelets and differential count [SOC]
 - b. Comprehensive metabolic panel [SOC]
 - c. Uric Acid
 - d. Total cholesterol
 - e. INR
- 4. Blood draw for Biomarker Analysis (including genetic biomarker testing ONLY if the subject consent is in place)
- 5. Transthoracic Echocardiogram
- 6. Handgrip strength (by dynamometer)
- 7. Gait Speed Test
- 8. 6 minute walk test
- 9. Maximal treadmill cardiopulmonary exercise test (as defined in REVIVAL MOP)
- 10. Quality of life and health utility questionnaires
- 11. Patient preference questionnaire
- 12. Caregiver consent (see MOP for details)
- 13. Obtain information needed to complete follow up eCRF
- 14. Outcome assessments for:
 - Hospitalizations
 - Stroke
 - MCSD
 - Transplant
 - Death (Cardiovascular related vs. Non-cardiovascular related)

If the heart failure subject has an historic ECG on file that was completed within 30 days of the assessment date, this may be used for fulfillment of this visit requirement if, in the opinion of the investigator, the historic ECG is highly likely to represent the subject's current health status.

If the heart failure subject has historic laboratory results on file that were drawn within 14 days of the Baseline B assessment date, these results may be used for fulfillment of this visit requirement if, in the opinion of the investigator, the historic laboratory result(s) are highly likely to represent the subject's current health status.

Core Laboratory Data Handling and Transfer (refer to MOP)

Following completion of the echocardiogram and cardiopulmonary exercise test, studies will be submitted for analysis by the Echocardiography Core Laboratory or Cardiopulmonary Exercise Core Laboratory.

Following completion of baseline B assessments, heart failure subjects will progress to the follow up phase of REVIVAL, with in-clinic follow up visits planned at six (6) months, twelve (12) months, eighteen (18) months and twenty four (24) months.

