6.2.3 Six (6) Month Follow up (+/- 45 days)

Standard of Care [SOC] testing will be included in the heart failure subject evaluation for this visit. All SOC procedures are labeled as such below. For the six (6) month follow up visit, subjects will undergo the following testing and evaluation:

- 1. Directed history and physical (including NYHA and INTERMACS Patient Profile)
- 2. Blood draw for:
 - a. CBC with platelets and differential count [SOC]
 - b. Comprehensive metabolic panel [SOC]
- 3. Handgrip strength (by dynamometer)
- 4. Gait Speed Test
- 5. 6 minute walk test
- 6. Quality of life and health utility questionnaires
- 7. Caregiver questionnaire collection (if applicable)
- 8. Obtain information needed to complete follow up eCRF
- 9. Outcome assessments for:
 - Hospitalizations
 - Stroke
 - MCSD
 - Transplant
 - Death (Cardiovascular related vs. Non-cardiovascular related)

If the heart failure subject has historic laboratory results on file that were drawn within 14 days of the assessment date, these results may be used for fulfillment of this visit requirement if, in the opinion of the investigator, the historic laboratory result(s) are highly likely to represent the subject's current health status.

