6.2.4 Twelve (12) Month Follow up (+/- 45 days)

Standard of Care [SOC] testing will be included in the heart failure subject evaluation for this visit. All SOC procedures are labeled as such below. For the twelve (12) month follow up visit, heart failure subjects will undergo the following testing and evaluation:

- 1. Directed history and physical (including NYHA and INTERMACS Patient Profile)
- 2. ECG [SOC]
- 3. Blood draw for:
 - a. CBC with platelets and differential count [SOC]
 - b. Comprehensive metabolic panel [SOC]
 - c. Uric Acid
 - d. Total cholesterol
 - e. INR
- 4. Handgrip strength (by dynamometer)
- 5. Gait Speed Test
- 6. 6 minute walk test
- 7. Quality of life and health utility questionnaires
- 8. Patient preference questionnaire
- 9. Caregiver questionnaire collection (if applicable)
- 10. Obtain information needed to complete follow up eCRF
- 11. Outcome assessments for:
 - Hospitalizations (Cardiovascular related vs. Non-cardiovascular related; Heart Failure related vs. Non-Heart Failure related) Stroke
 - VAD
 - Transplant
 - Death (Cardiovascular related vs. Non-cardiovascular related)

If the heart failure subject has an historic ECG on file that was completed within 30 days of the assessment date, this may be used for fulfillment of this visit requirement if, in the opinion of the investigator, the historic ECG is highly likely to represent the subject's current health status.

If the heart failure subject has historic laboratory results on file that were drawn within 14 days of the assessment date, these results may be used for fulfillment of this visit requirement if, in the opinion of the investigator, the historic laboratory result(s) are highly likely to represent the subject's current health status.

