Appendix A: Time and Event Schedule

Event/Assessment	Baseline A	Baseline B*	+/- 45 days			+/- 30 days
			6-Month Visit	12- Month Visit	18- Month Visit	24-Month Visit
6-Minute walk test	Х	Х	Х	Х	Х	X
Blood draw – Labs	X**	X**	Х	X**	Х	Х
Blood draw – Biomarker and Genetic testing		X				
Caregiver questionnaire		Х	Х	Х	Х	Х
Concomitant Medication	Х	Х	Х	Х	Х	Х
Demographics	Х					
Directed history and physical exam (including NYHA and INTERMACS profiles)	X	X	x	X	X	X
Dispense Patient Diary	Х					
ECG	Х	Х		Х		
Gait speed test	Х	Х	Х	Х	Х	Х
Handgrip strength test	Х	Х	Х	Х	Х	X
Heart Failure Survival Score (HFSS)		X				
Maximal treadmill CPX test		X				
QOL and health utility questionnaires	х	Х	X	Х	X	Х
Seattle Heart Failure Model (SHFM) Score ***	Х	X		Х		
Transthoracic Echo		X				
Outcome assessments		Х	Х	Х	Х	Х

*To take place 8 weeks (+/- 30 days) after consent **In addition to standard of care labs (CBC and Comprehensive Metabolic Panel) study-specific (nonstandard of care) labs are uric acid, total cholesterol and INR

*** Calculated and entered by DCC

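### The patient preference questionnaire is due at all six visits in Section 4.14 but is missing from the 6- and 18-month lists in Section 6.2, and Appendix A does not settle which applies

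*Protocol*

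**What the plan says.** Three places in the protocol bear on when the preference survey (the MEDAMACS VAD Survey, item e of the Section 4.14 list) is given.

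- **Section 4.14** gives a general rule: "The patient preference questionnaires will also be administered at all visits". Section 3.4 fixes what all visits means: "Clinic visits: Baseline A, Baseline B and follow up visits at 6,12,18 and 24 months".
- **Section 6.2** lists the procedures visit by visit. The survey is a numbered item of its own at baseline A ("8. Patient preference questionnaire"), at baseline B ("11. Patient preference questionnaire"), at 12 months ("Patient preference questionnaire") and at 24 months. At 6 and 18 months the list goes from item 6, "Quality of life and health utility questionnaires", straight to item 7, the caregiver questionnaire.
- **Appendix A** has a row for "QOL and health utility questionnaires", marked at all six visits, and another for the caregiver questionnaire. It has none named for patient preferences.

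Section 3.4 sends the reader to Section 6.0 and Appendix A for what is done at each visit.

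**The concern.** A site cannot follow both Section 4.14 and Section 6.2: doing what the 6- and 18-month lists say breaks the Section 4.14 rule. Appendix A, where one would look for the answer, does not mention the survey by name.

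The survey supplies the patients' end-of-life preferences and their thresholds for considering a VAD. Section 8.3.2 describes preferences as an outcome followed over time. Objective 3 and Section 8.4 plan to relate preferences and thresholds to caregiver burden, which is scheduled at 6 and 18 months. If the survey is skipped at those visits, the burden scores have no preference measurement from the same visit. Under Section 3.2, follow-up stops at death, transplant or durable VAD. For a subject who reaches one of these between months 6 and 12, or between months 18 and 24, the skipped survey would have been the last one before the endpoint and cannot be recovered.

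**Working it through.** The protocol states no figure to reproduce here. The check is a count by visit from Sections 3.4, 4.12, 4.14, 6.2.1 to 6.2.6, Objective 3 in Section 2.0, and Appendix A.

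| Visit | Survey, 4.14 | Survey, 6.2 | Caregiver burden (Objective 3) | SHFM (4.12) |
|---|---|---|---|---|
| Baseline A | yes | yes (item 8) | no | yes |
| Baseline B | yes | yes (item 11) | yes | yes |
| 6 months | yes | **no** | yes | no |
| 12 months | yes | yes (item 8) | yes | yes |
| 18 months | yes | **no** | yes | no |
| 24 months | yes | yes (item 7) | yes | no |

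**Is the gap a fault of the text extraction?** No. The lists in 6.2.3 and 6.2.5 are numbered 1 to 9 without a break, so no item has dropped out.

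**Preference time points.** Section 4.14 gives 6 of 6. Section 6.2 gives 4 of 6, so 2/6 = 33% fewer.

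**Visits with both burden and preferences.** Burden is scheduled at 5 visits (baseline B, 6, 12, 18 and 24 months). Under Section 4.14 all 5 are paired. Under Section 6.2 the pairs are baseline B, 12 and 24 months: 3 of 5, so 2/5 = 40% fewer.

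**Spacing.** Take baseline B at its nominal 2 months and assume that visit months count from enrolment. From baseline B on, the gaps between surveys are then:

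- Section 4.14: 6 − 2 = 4, 12 − 6 = 6, 18 − 12 = 6 and 24 − 18 = 6 months.
- Section 6.2: 12 − 2 = 10 and 24 − 12 = 12 months.

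**Visits with both modelled prognosis and preferences (Objective 2).** The Seattle score is calculated at baseline A, baseline B and 12 months, and the Heart Failure Survival Score at baseline B only (Section 4.13). All 3 Seattle visits list the survey under Section 6.2, so 3 of 3 pairs survive.

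**Appendix A.** Read literally, it shows the survey at 0 of 6 visits. If the quality-of-life row is taken to include it, it shows 6 of 6. Neither count is the 4 of 6 in Section 6.2, so no reading makes all three places agree.

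**The case against.** The strongest reply is that this is a wording conflict over two visits with modest consequences. Several parts of that reply stand.

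- **Objective 2 is largely protected.** Section 8.4 uses end-of-life preferences as a predictor of whether a patient considers a VAD, so they are not the modelled outcome there. No new modelled prognosis is produced at 6 or 18 months under either schedule. A reader might infer that Objective 2 loses a third of its data in a way that defeats it; the documents do not support that.
- **Objective 3 does not demand a pair at every visit.** Its wording asks for preferences to be related to burden, and three paired visits remain. The model has less information but can still be fitted.
- **Appendix A can be read as covering the survey.** Section 4.14 introduces the survey within its list of health status and quality-of-life assessments. A reader might infer that a site working from Appendix A alone would collect no preference data. That is a worst case: the quality-of-life row may include the survey, and Section 3.4 points to Section 6.0 together with Appendix A.
- **Section 6.2 may be deliberate.** Both baselines and then once a year is a coherent pattern.

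The conflict itself survives. Section 6.2 separates the survey from the quality-of-life item at four visits and drops only the survey at the other two, so the quality-of-life item at 6 and 18 months cannot be assumed to contain it. If the annual pattern was intended, Section 4.14 is wrong as written.

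Two further inferences are tempting. One is that collection will differ between sites. Central electronic forms, site training and edit checks by the coordinating center (Sections 16.1, 17.0 and 17.3) make uniform collection at least as plausible, and the manual of procedures is not available to settle it. The other is that the gaps would be missing not at random. A survey omitted because of a schedule does not depend on the patient's unobserved preference, so nothing here goes beyond the missing-at-random methods of Section 8.1.

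**Conclusion.** The protocol contradicts itself on when the preference survey is given, and the point should be corrected. If Section 6.2 governs, the survey is taken at 4 of 6 visits rather than 6, and accompanies caregiver burden at 3 of 5 visits rather than 5. The loss falls on the Objective 3 model of preferences on burden and on the description of preferences over time in Section 8.3.2. The effect on Objective 2 is smaller, since all three Seattle score visits keep the survey.

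These counts describe the schedule, before attrition, optional caregiver participation, and the omission of forms for subjects without English proficiency. They assume that Section 6.2 is what sites carry out. The protocol does not show which schedule was intended, and the case report forms and manual, which might, are not at hand. The contradiction does not depend on that assumption; the size of the loss does.

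**What to change.** Bring Sections 4.14, 6.2.3, 6.2.5 and Appendix A to one schedule. The better choice is to add the patient preference questionnaire to the 6- and 18-month lists: this agrees with Section 4.14 and pairs the survey with caregiver burden at all five burden visits. If the sparser schedule was intended, restrict Section 4.14 to baseline A, baseline B, 12 and 24 months and accept three paired visits. In either case give the questionnaire its own row in Appendix A, separate from the quality-of-life row. Which time points enter each model can be left to the SAP.

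The cost is a minor amendment. The preferred option adds one questionnaire at each of two visits that Section 3.4 already holds in person, so at most 2 extra forms per subject relative to Section 6.2, and none relative to Section 4.14.
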